### 8.1. Endpoint / Variables

#### 8.1.1. Drug Concentration Measures

Refer to [Appendix 4](#) Data Display Standards & Handling Conventions (Section 11.4.3 Reporting Standards for Pharmacokinetic)

#### 8.1.2. Derived Pharmacokinetic Parameters

Pharmacokinetic parameters will be calculated by standard non-compartmental analysis according to current working practices and using the currently supported version of WinNonlin. All calculations of non-compartmental parameters will be based on actual sampling times.

Pharmacokinetic parameters listed in [Table 1](#) will be determined from the plasma concentration-time data, as data permits, for each subject, analyte (total radioactivity, GSK2269557 and [C]-GSK2269557) and treatment period unless otherwise stated.

Pharmacokinetic parameters listed in [Table 2](#) will be determined from the urine and faeces concentration-time data, as data permits, for each collection interval, subject and treatment period unless otherwise stated.

**Table 1** **Derived Plasma Pharmacokinetic Parameters**

Parameter	Parameter Description
AUC(0-t)	Area under the concentration-time curve from time zero to the time of the last quantifiable concentration (C(t)) will be calculated using the linear trapezoidal rule for each incremental trapezoid and the log trapezoidal rule for each decremental trapezoid.
AUC(0-24)	Area under the concentration-time curve from time zero to 24 hours post dose (C(t)) will be calculated using the linear trapezoidal rule for each incremental trapezoid and the log trapezoidal rule for each decremental trapezoid.
AUC(0-∞)	Area under the concentration-time curve extrapolated to infinity will be calculated as: $AUC = AUC(0-t) + C(t) / \lambda_z$
%AUCex	The percentage of AUC (0-∞) obtained by extrapolation (%AUCex) will be calculated as: $[\text{AUC}(0-\infty) - \text{AUC}(0-t)] / \text{AUC}(0-\infty) \times 100$
Cmax	Maximum observed concentration, determined directly from the concentration-time data.
tmax	Time to reach Cmax, determined directly from the concentration-time data.
t½	Apparent terminal half-life will be calculated as: $t_{1/2} = \ln 2 / \lambda_z$
CL(iv)	Total iv clearance will be calculated as: $CL(iv) = \text{Dose(iv)} / \text{AUC}(0-\infty)$ Treatment period 1, analyte [  C]-GSK2269557 only where Dose(iv) is the actual iv dose calculated as [weight of full syringe (g) minus syringe weight after dose (g)] multiplied by nominal concentration (μg/g)
CLr	If Plasma AUC(0-∞) is calculable then $CL_r = \text{Cumulative Ae[urine]} / \text{Plasma AUC}(0-\infty)$ If Plasma AUC(0-∞) is not calculable then $CL_r = \text{Cumulative Ae[urine]} / \text{Plasma AUC}(0-t)$ Where cumulative Ae from excretion data for treatment period 1 and AUC from NCA PK analysis of Treatment period 1, analyte [  C]-GSK2269557 only.
V(c)	Dose(IV) / AUC(0-∞) Treatment period 1, analyte [  C]-GSK2269557 only. Where Dose(IV) is the radiometric dose as described in Table 1 .
V(dss)	Dose(IV) × AUMC(0-∞) / (AUC(0-∞)) Treatment period 1, analyte [  C]-GSK2269557 only. Where AUMC is the area under the moment curve and Dose(IV) is the radiometric dose as described in Table 1 .

Parameter	Parameter Description
ML(iv)	
Metabolite load following intravenous administration is calculated as:
 $\frac{\text{Total Radioactivity AUC}(0-\infty) - [\text{14C}]\text{-GSK2269557 AUC}(0-\infty)}{\text{Total Radioactivity AUC}(0-\infty)}$ 
Treatment period 1 only

ML(po)	
Metabolite load following oral administration is calculated as:
 $\frac{\text{Total Radioactivity AUC}(0-\infty) - \text{GSK2269557 AUC}(0-\infty)}{\text{Total Radioactivity AUC}(0-\infty)}$ 
Treatment period 2 only.
 
Note: GSK2269557 AUC(0-∞) may be updated depending on the sample analysis conducted but refers to the parent GSK2269557 from oral dose.

Fg	
Fraction metabolised by gut wall as a fraction of the oral dose will be calculated as follows:
 $Fg = 1 - (ML(po) - ML(iv))$
E H	
Hepatic extraction ratio is calculated (Davis, B et al, 1993) as follows:
 $E_H = CL(iv)/1450 \text{ mL/min}$
F abs	
Fraction absorbed following an oral dose is calculated as follows:
 $F_{abs} = \frac{\text{Oral F}(0-\infty)}{1 - E_H} / F_g$
Dose(IV)	Radiometric IV dose will be calculated by Covance
Dose(oral)	Radiometric Oral dose will be calculated by Covance
Dose(inhaled)	Nominal inhaled dose
Oral F (0-∞)	
Oral absolute bioavailability based on AUC(0-∞) calculated as:
 $\frac{\text{GSK2269557 AUC}(0-\infty)(\text{oral})}{\text{Dose}(\text{oral})} / \frac{[\text{14C}]\text{-GSK2269557 AUC}(0-\infty)(\text{iv})}{\text{Dose}(\text{iv})}$ 
Per subject.
 
Note: Radiometric dose will be used for oral and iv as described in Table 1. GSK2269557 AUC(0-∞)(oral) may be updated depending on the sample analysis

Parameter	Parameter Description
	conducted but refers to the parent GSK2269557 from oral dose.
Inhaled F (0-∞)	
Inhaled absolute bioavailability based on AUC(0-∞) calculated as
 $\frac{\text{GSK2269557 AUC(0-∞) (inhaled)}}{\text{Dose (inhaled)}} \Bigg/ \frac{[14\text{C}]\text{-GSK2269557 AUC(0-∞) (iv)}}{\text{Dose (iv)}}$ 
Per subject.
 
Note: Radiometric dose will be used for oral and iv as described in Table 1.

Oral F (0-t)	
Oral absolute bioavailability based on AUC(0-t) calculated as:
 $\frac{\text{GSK2269557 AUC(0-t) (oral)}}{\text{Dose (oral)}} \Bigg/ \frac{[14\text{C}]\text{-GSK2269557 AUC(0-t) (iv)}}{\text{Dose (iv)}}$ 
Per subject.
 
Note: Radiometric dose will be used for oral and iv as described in Table 1.. GSK2269557 AUC(0-∞)(oral) may be updated depending on the sample analysis conducted but refers to the parent GSK2269557 from oral dose.

Inhaled F (0-t)	
Inhaled absolute bioavailability based on AUC(0-t) calculated as
 $\frac{\text{GSK2269557 AUC(0-t) (oral)}}{\text{Dose (oral)}} \Bigg/ \frac{[14\text{C}]\text{-GSK2269557 AUC(0-t) (iv)}}{\text{Dose (iv)}}$ 
Per subject.
 
Note: Radiometric dose will be used for oral and iv as described in Table 1.

GSK2269557 /Total radioactivity ratio for Cmax,	
Cmax Ratio = <math>\text{Exp} \{ [\text{log}(GSK2269557 \text{ Cmax})] - [\text{log}(\text{Total radioactivity Cmax})] \}</math>
 
Per subject for radiolabelled oral dose. GSK2269557 may be updated depending on the sample analysis conducted but refers to the parent GSK2269557 from oral dose

GSK2269557 /Total radioactivity ratio for AUC(0-inf)	
AUC(0-inf) Ratio = <math>\text{Exp} \{ [\text{log}(GSK2269557 \text{ AUC(0-inf)})] - [\text{log}(\text{Total radioactivity AUC(0-inf)})] \}</math>
 
Per subject for radiolabelled oral dose. GSK2269557 may be updated depending on the sample analysis conducted but refers to the parent GSK2269557 from oral dose

GSK2269557 /Total radioactivity	
AUC(0-t) Ratio = <math>\text{Exp} \{ [\text{log}(GSK2269557 \text{ AUC(0-t)})] - [\text{log}(\text{Total radioactivity AUC(0-t)})] \}</math>

Parameter	Parameter Description
ratio for AUC(0-t)	Per subject for radiolabelled oral dose. GSK2269557 may be updated depending on the sample analysis conducted but refers to the parent GSK2269557 from oral dose
[  C]-GSK2269557 /Total radioactivity ratio for Cmax,	Cmax Ratio = Exp { [loge([  C]-GSK2269557 Cmax] - [loge(Total radioactivity Cmax]) } Per subject for radiolabelled IV dose.
[  C]-GSK2269557 /Total radioactivity ratio for AUC(0-inf)	AUC(0-inf) Ratio = Exp { [loge([  C]-GSK2269557 AUC(0-inf)] - [loge(Total radioactivity AUC(0-inf)) } Per subject for radiolabelled IV dose.
[  C]-GSK2269557 /Total radioactivity ratio for AUC(0-t)	AUC(0-t) Ratio = Exp { [loge([  C]-GSK2269557 AUC(0-t)] - [loge(Total radioactivity AUC(0-t)) } Per subject for radiolabelled IV dose.

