12. APPENDICES

12.1. Appendix 1: Abbreviations and Trademarks

Abbreviations	
ADME	Absorption Distribution Metabolism Excretion
AE	Adverse Event
ALT	Alanine aminotransferase (SGPT)
AMS	Accelerator Mass Spectrometry
APE	All Participants Enrolled
AST	Aspartate aminotransferase (SGOT)
AUC	Area under concentration-time curve
AUC(0- inf)	Area under the concentration-time curve from time zero (pre-dose) extrapolated to infinite time
AUC(0-t)	Area under the concentration-time curve from time zero (pre-dose) to last time of quantifiable concentration within a participant across all treatments
BMI	Body mass index
BP	Blood pressure
BPM	Beat Per Minute
Bq	Becquerel
C	Carbon
Ci	Curie
CIOMS	Council for International Organizations of Medical Sciences
C _{max}	Maximum observed concentration
CO	Carbon Monoxide
CO ₂	Carbon dioxide
CONSORT	Consolidated Standards of Reporting Trials
COPD	Chronic obstructive pulmonary disease
CPK	Creatine phosphokinase
CPM	Clinical Project Manager
CRF	Case Report Form
CT	Computed Tomography
δ	Delta
DMPK	Drug Metabolism and Pharmacokinetics
DNA	Deoxyribonucleic acid
ECG	Electrocardiogram
EDTA	Ethylenediaminetetraacetic acid
F	Absolute bioavailability
FDA	Food and Drug Administration
GCP	Good Clinical Practice
GI	Gastrointestinal
GSK	GlaxoSmithKline
h	Hour(s)
HDPE	High Density Polyethylene
HPLC	High-performance liquid chromatography

Abbreviations	
HBsAg	Hepatitis B surface antigen
HIPAA	Health Insurance Portability and Accountability Act
HIV	Human Immunodeficiency Virus
HR	Heart rate
HMR	Hammersmith Medicines Research
IB	Investigator's Brochure
ICF	Informed consent form
ICH	International Conference on Harmonization of Technical Requirements for Registration of Pharmaceuticals for Human Use
ICRP	International Commission on Radiological Protection
IDSL	Integrated Data Standards Library
IEC	Independent Ethics Committee
IgE	Immunoglobulin E
IgM	Immunoglobulin M
IMP	Investigational medicinal product
INR	International normalized ratio
IP	Investigational Product
IRB	Institutional Review Board
IV	Intravenous
IVIVT	In vitro/In vivo Translation
kBq	Kilo Becquerel
Kg	Kilogram
λ_z	Terminal phase rate constant
L	Litre
LDH	Lactate dehydrogenase
LSC	Liquid Scintillating Counting
μCi	Micro Curie
μg	Microgram
μSv	Micro Sievert
m	Meter
MBq	Megabecquerel
MCH	Mean corpuscular haemoglobin
MCHC	Mean corpuscular haemoglobin concentration
MCV	Mean corpuscular volume
MDD	Medical Devices Directive
MgSt	Magnesium stearate

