## 2. SUMMARY OF KEY PROTOCOL INFORMATION

### 2.1. Changes to the Protocol Defined Statistical Analysis Plan

There were no changes or deviations to the originally planned statistical analysis specified in the protocol amendment 1 [(Dated: 30/Oct/2017)], however additional PK parameters have been requested.

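### AUC(0-t) has a different end time in the protocol and the SAP, and the difference is not declared, so F(0-t) can divide exposures measured over unequal windows

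*SAP*

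**What the plan says.** **Protocol, Appendix 1 (abbreviations).** AUC(0-t) is "Area under the concentration-time curve from time zero (pre-dose) to last time of quantifiable concentration within a participant across all treatments". Read plainly, each participant has one end time, shared by both treatment periods.

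**SAP, Table 1.** AUC(0-t) is "Area under the concentration-time curve from time zero to the time of the last quantifiable concentration (C(t". The phrase about participants and treatments is absent. Section 8.1.2 says the Table 1 parameters are derived "as data permits, for each subject, analyte (total radioactivity, GSK2269557 and" the labelled parent) and treatment period. Each profile therefore has its own end time.

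**SAP, Section 2.1.** "There were no changes or deviations to the originally planned statistical analysis specified in the protocol amendment 1". The only qualification is that extra PK parameters have been requested.

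**Where it is used.** Table 1 has an entry headed "Oral absolute bioavailability based on AUC(0-t) calculated as", which divides dose-normalised oral AUC(0-t) from period 2 by dose-normalised IV AUC(0-t) from period 1. Inhaled F(0-t) is a companion entry. The parent/total radioactivity ratios, including the one marked "Per subject for radiolabelled IV dose", also divide one AUC(0-t) by another. No rule in the SAP aligns the two end times.

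**The concern.** A bioavailability ratio is interpretable when numerator and denominator cover comparable parts of the concentration curve. SAP Section 8 expects the IV parent to be read by LC+AMS, and the inhaled and oral parent by LC/MS. The doses are 10 µg IV, 1000 µg inhaled and 800 µg oral. With different assays and doses 80 to 100 times apart, the last quantifiable samples need not coincide. Late plasma samples are sparse in both periods (24, 48, 72, 96 and 168 h), so losing a single late sample shortens a window by 24 to 72 h.

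If the end times differ, F(0-t) mixes the fraction reaching the circulation with how long each assay could follow the drug. Absolute bioavailability is a secondary endpoint. F(0-∞) is also planned, but AUC(0-∞) is derived only as data permit and no F based on AUC(0-24) is planned. A participant without a usable terminal slope would therefore have F(0-t) as the only available estimate.

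**Working it through.** **1. Text.** The documents give no figure to reproduce. The protocol's end time belongs to the participant; the SAP's belongs to the subject-by-analyte-by-period profile. The two agree only when the profiles being compared happen to end at the same time.

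**2. Which ratios the protocol wording reaches.** It speaks of treatments, not analytes.
- Oral F(0-t) compares period 2 with period 1, so it is reached directly.
- Inhaled F(0-t) compares two analytes within the period 1 treatment, so it is not clearly reached, although the window problem is the same. As printed, its formula has the oral AUC and oral dose in the numerator. That is a separate error; here it is read with inhaled terms, as in Inhaled F(0-∞).
- The parent/total ratios compare analytes within one period and are among the later additions, so they are not reached.

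**3. Size, closed form.** Assume mono-exponential decline with rate k = ln 2 / half-life. Then AUC(0-T) is proportional to 1 − exp(−kT), and

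F(0-t) / equal-window F = [1 − exp(−k·t_oral)] / [1 − exp(−k·t_IV)].

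The half-lives and last times are assumptions, because the documents give neither a half-life nor a quantification limit. Both 48 h and 168 h are scheduled samples. With oral ending at 48 h and IV at 168 h:

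| Half-life | Numerator | Denominator | Ratio | Shift |
|---|---|---|---|---|
| 12 h | 0.9375 | 0.9999 | 0.938 | −6% |
| 24 h | 0.7500 | 0.9922 | 0.756 | −24% |
| 48 h | 0.5000 | 0.9116 | 0.548 | −45% |

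Swapping the two end times inverts the ratios: 1/0.938 = 1.07, 1/0.756 = 1.32, 1/0.548 = 1.82.

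**4. Size, on the protocol's sampling grids.** Noise-free one-compartment profiles were used, with true F = 1, a 15-minute infusion, an assumed absorption rate of 1/h, and the SAP's linear-up/log-down rule. F(0-t) with each profile's own end time:

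| Last times | 12 h | 24 h | 40 h | 60 h |
|---|---|---|---|---|
| IV 168, oral 168 | 0.998 | 0.999 | 0.998 | 0.998 |
| IV 168, oral 96 | 0.994 | 0.942 | 0.853 | 0.778 |
| IV 96, oral 168 | 1.002 | 1.057 | 1.165 | 1.276 |
| IV 96, oral 48 | 0.935 | 0.791 | 0.687 | 0.625 |
| IV 48, oral 96 | 1.060 | 1.248 | 1.431 | 1.567 |

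(Columns are assumed half-lives.) Cutting both profiles at the earlier end time gives 0.985 to 0.999 in all these cases.

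**5. Cost of a common window.** At a half-life of 48 h, cutting the IV profile from 168 h to 48 h lowers its captured share of AUC(0-∞) from 1 − 2^(−3.5) = 91% to 1 − 2^(−1) = 50%.

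**The case against.** The protocol wording sits only in an abbreviation list. Protocol Section 10.3.1 plans AUC(0-t) by non-compartmental methods with no common-time rule, and Appendix 1 does not say whether the earliest or the latest last time governs. If the latest, the shorter profile would have to be integrated beyond its own quantifiable data. An end time specific to each profile is also what AUC(0-∞) = AUC(0-t) + C(t)/λz and %AUCex require. All of this stands. It means that simply restoring the protocol wording is not a good remedy.

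The study tests no hypotheses, has about six participants, and already plans F(0-∞), AUC(0-∞) ratios, AUC(0-24) ratios, %AUCex and full listings. The assays may be adapted, so even the sensitivity mismatch is conditional. This also stands and limits the impact.

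For the parent/total ratios, truncation is debatable in itself. If total radioactivity outlasts parent, stopping both at parent's last time discards late metabolite exposure and raises the ratio. The AUC(0-24) ratio already provides equal windows.

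None of this explains the statement in SAP Section 2.1, and none of it supplies an end-time rule for F(0-t).

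**Conclusion.** There is a real, undeclared difference between the two definitions. Followed as written, the SAP allows Oral F(0-t) and Inhaled F(0-t) to be ratios over unequal windows. It merits correction because the affected quantity is a secondary endpoint and the correction is cheap. The difference in wording is certain; the size of its effect is not known.

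A reader might infer more than the documents support:
- **That the windows will differ.** They differ only if last quantifiable times differ. If both profiles reach the same time there is no bias.
- **That F(0-t) is low by 6 to 45%.** Those figures follow from assumed half-lives and one assumed pair of end times. Other pairs give no shift or a shift upwards.
- **That F(0-t) is the plan's designated fallback.** The SAP writes an AUC(0-t) fallback only for CLr. Both versions of F are listed together in Table 2.13 without ranking, and Fabs uses F(0-∞) alone.
- **That the parent/total ratios breach the protocol definition.** The definition covers treatments, not analytes.

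**What to change.** 1. Keep each profile's own AUC(0-t) for AUC(0-∞), %AUCex and the AUC(0-t) endpoint summaries.
2. For Oral F(0-t) and Inhaled F(0-t), define a separately named partial AUC. Compute it for both routes up to the last time at which both of that participant's profiles are quantifiable, and report that time.
3. State in SAP Section 2.1 that AUC(0-t) is defined differently from protocol Appendix 1, and why.
4. For the parent/total AUC(0-t) ratios, name the planned AUC(0-24) ratio as the equal-window comparison, and footnote the last quantifiable time of each analyte.

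The cost is a few lines of SAP text and one extra partial-AUC run. The real downside is a materially shorter window for some participants, as step 5 of the working shows, so the common-window F(0-t) should be read alongside F(0-∞).

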2.8.	PK	PK05	Summary of Log-Transformed Derived Plasma [14C]-GSK2269557 PK Parameters by Treatment	
Include columns for parameter, period, treatment, N, n, geometric mean, 95% CI of geometric mean, standard deviation (SD) of logged data, median, minimum, maximum and between subject geometric coefficient of variation (CVb (%)).
 
Refer to Section 11.4.3 for parameters that should be log transformed. In addition to standard [14C]-GSK2269557 pk parameters include Clearance (CL(iv) and CLr) and volume (Vdss and Vc).
 
refer to  gsk2269557/pii115119/part_a/drivers/t_pk_sum_log (Table 4.3)
	SAC
2.9.	PK	PK01	Summary of Plasma GSK2269557 Concentrations by Treatment and Time	Include untransformed concentrations	SAC
2.10.	PK	Refer to Programming Notes	Summary of Log Transformed Plasma GSK2269557 Concentrations by Treatment and Time	Include log transformed concentrations use standard macro for sumstatsinrows for log transformed variable, present similar to example shell PK01 but present geometric mean and SD (Log) rather than mean and SD respectively.	SAC
2.11.	PK	PK03	Summary of Derived Plasma GSK2269557 PK Parameters by Treatment	Include columns for parameter, period, treatment, N, n, arithmetic mean, 95% CI of arithmetic mean, standard deviation (SD), median, minimum and maximum.	SAC

Pharmacokinetic: Tables					
No.	Population	IDSL / TST ID / Example Shell	Title	Programming Notes	Deliverable
2.12.	PK	PK05	Summary of Log-Transformed Derived Plasma GSK2269557 PK Parameters by Treatment	
Include columns for parameter, period, treatment, N, n, geometric mean, 95% CI of geometric mean, standard deviation (SD) of logged data, median, minimum, maximum and between subject geometric coefficient of variation (CVb (%)).
 
Refer to Section 11.4.3 for parameters that should be log transformed
 
refer to gsk2269557/pii115119/part_a/drivers/t_pk_sum_log (Table 4.3)
	SAC
2.13.	PK	PK06	Summary of Oral and Inhaled Absolute Bioavailability	
Refer to Section 11.4.3 for parameters that should be log transformed.
 
Include PK Parameters: Inhaled F (0-∞), Inhaled F (0-t), Oral F (0-∞) and Oral F (0-t), Dose(Inhaled), Dose(iv) and Dose(Oral).
 
Note: Dose(iv) and Dose(Oral) is radiometric dose, Dose(Inhaled) is nominal
	SAC

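### SAP Table 1 gives V(c) the clearance formula, and the CL(iv) row defines the IV dose differently from the V and F rows

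*SAP*

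**What the plan says.** SAP section 8.1.2 opens by saying "Pharmacokinetic parameters will be calculated by standard non-compartmental analysis", and Table 1 then gives a formula for each plasma parameter. Three rows apply to period 1 and analyte [14C]-GSK2269557 only:

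- CL(iv) is IV dose over AUC(0-∞); with its markup the row reads "Dose(iv)} / \text{AUC}(0-\infty)$ Treatment period 1". The row takes its dose as full syringe weight "minus syringe weight after dose (g)] multiplied by nominal concentration".
- V(c) is printed as IV dose over AUC(0-∞). Its dose note reads "Where Dose(IV) is the radiometric dose as described in" Table 1.
- V(dss) is IV dose times AUMC(0-∞) over the square of AUC(0-∞), with the same radiometric dose note.

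The Dose(IV) row of Table 1 says "Radiometric IV dose will be calculated by Covance". The notes to the oral and inhaled F rows say "Radiometric dose will be used for oral and iv as described in Table 1". The programming note for Table 2.13 (SAP 11.9.5) says "Dose(iv) and Dose(Oral) is radiometric dose, Dose(Inhaled) is nominal".

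The notes under Table 1 have CL, Vdss and Vc derived in Phoenix and passed to the statistics and programming group. The radiometric doses go to that same group, which derives E_H, F_abs and F. V(c) is not among the programmer-derived parameters in SAP 11.4.3.

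SAP 8.3.2 names Vdss and Vc as the volumes to be summarised and listed. They appear in Tables 2.7 and 2.8 and in Listing 34. Protocol section 4 lists volume and clearance after the IV dose as a secondary endpoint without naming V(c).

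**The concern.** Two rows with different names, one a clearance and one a volume, carry the same expression. If the V(c) row were followed literally, a reported volume for a secondary endpoint would be a clearance under another label. If it is not followed, the SAP gives no means of knowing which volume the number represents.

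The second issue is that one symbol stands for two quantities. The F formulas print the dose with the same label as the CL(iv) row, but their notes assign it the radiometric value. CL(iv) feeds E_H = CL(iv)/1450 mL/min. E_H in turn feeds F_abs = Oral F/(1 − E_H)/Fg, where Oral F is on the radiometric dose. At stake is whether CL(iv), E_H, F_abs (Table 2.14, Listing 38) and F can be read together as one consistent set.

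**Working it through.** The plan states no numerical result for these parameters, so there is no figure to reproduce. The check covers units, a model example, a comparison of dose definitions, and the route from CL(iv) to F_abs.

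**1. Units.** With dose in µg and AUC in ng·h/mL, which equals µg·h/L:

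- V(c) as printed: µg ÷ (µg·h/L) = L/h, a clearance.
- V(dss) as printed: µg × (µg·h²/L) ÷ (µg·h/L)² = L, a volume.

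**2. Does the V(c) expression respond to the central volume?** Take a two-compartment model with 10 µg infused over 0.25 h (Protocol 5.1.2). The other values are assumed: CL 20 L/h, intercompartmental clearance 60 L/h and peripheral volume 500 L.

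| True Vc (L) | True Vss (L) | V(c) row returns | V(dss) row returns |
|---|---|---|---|
| 10 | 510 | 20.0 L/h | 512.5 L |
| 50 | 550 | 20.0 L/h | 552.5 L |
| 200 | 700 | 20.0 L/h | 702.5 L |

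The V(c) row returns CL whatever the central volume is. The V(dss) row follows the true volume. Its constant 2.5 L excess is CL times half the infusion time (20 × 0.125 h), which arises because the printed form makes no infusion correction. That is a separate matter and small in this example.

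**3. The same with the protocol's planning figures.** Footnote 1 to Protocol Table 1 (section 5.5.1) predicts a Period 1 AUC(0-24h) of 14.7 ng·h/mL and takes IV exposure as 1% of inhaled. The IV part is 14.7 × 0.01/1.01 = 0.1455 ng·h/mL. Using this in place of AUC(0-∞), 10 µg ÷ 0.1455 µg·h/L = 68.7 L/h. The CL(iv) and V(c) rows would both return this number.

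**4. Dose definitions side by side.**

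| SAP entry | IV dose used |
|---|---|
| Table 1, CL(iv) | syringe weight change × nominal concentration |
| Table 1, V(c) and V(dss) | radiometric |
| Table 1, Dose(IV) | radiometric |
| Table 1, notes to oral and inhaled F | radiometric |
| 11.9.5, Table 2.13 note | radiometric |

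CL(iv) is the only exception, and the SAP gives no reason for it.

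**5. Route into E_H and F_abs.** Let g be the syringe-weight dose divided by the radiometric dose, and E the extraction ratio on the radiometric dose. As written, CL(iv) and E_H are g times their radiometric values. Oral F and Fg do not depend on g. So

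F_abs as written ÷ F_abs on one dose basis = (1 − E)/(1 − gE).

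The documents give neither g nor E. With assumed values, for illustration only:

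| E | g = 0.90 | g = 0.95 | g = 1.05 | g = 1.10 |
|---|---|---|---|---|
| 0.2 | 0.976 | 0.988 | 1.013 | 1.026 |
| 0.5 | 0.909 | 0.952 | 1.053 | 1.111 |

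At g = 1 every entry is 1.

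**The case against.** The strongest defence is that Table 1 is not what produces V(c). Phoenix does, by its own non-compartmental routine, and V(c) is absent from the list that programmers build from the SAP formulas. V(dss) is dimensionally sound and reported alongside it, the CL(iv) expression is correct, and the protocol endpoint asks only for volume and clearance. This stands as far as the output goes: a reader might infer that the reported V(c) will be wrong, and the documents do not show that. It does not repair the SAP, whose only definition of a reported parameter is not a volume.

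On the dose, the SAP does not describe how the radiometric dose is calculated. It may itself use the delivered syringe weight, and the two doses may nearly agree. That also stands, and it is why no size can be given.

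A reader might also infer that CL(iv) and V(dss) will be reported on different doses. That follows from the printed rows but not from the workflow. The Table 1 notes put both in the same Phoenix derivation without saying which dose is entered. The split could instead be CL and V on one dose and F on the other.

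Finally, it is tempting to use the protocol's planning exposures to cap E_H, and hence the F_abs discrepancy. They do not support a cap:

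- Taking IV exposure as 1% of inhaled implies inhaled F = 1 and E_H = 1145/1450 = 0.79.
- Otherwise CL = 1145 × F mL/min, so E_H = 0.79 × F. With 60:40 deposition, complete lung absorption and the predicted Period 2 AUC of 3.7 ng·h/mL, the dose-normalised oral-to-inhaled ratio is (3.7/800)/(14.55/1000) = 0.318. Then F = 0.6/(1 − 0.4 × 0.318) = 0.687 and E_H = 0.54.
- With 60:40 deposition and the 23% oral share from the charcoal-block study, F = 0.6/0.77 = 0.779 and E_H = 0.62.

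These disagree. The second implies an oral share of 0.4 × 0.318 = 12.7%, against the stated 23%. All rest on extrapolated geometric means, which cannot bound six individual values.

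**Conclusion.** Both points hold as faults in the SAP text. The V(c) row prints a clearance, and no other part of the SAP defines V(c). Whether the reported value will be affected is not shown, because Phoenix derives it. If Phoenix returns a true volume, the SAP formula is wrong and the volume unidentified.

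The CL(iv) row uses a different IV dose from every other entry, so as written F_abs mixes two dose bases through E_H. The size of this is unknown and may be negligible. The factors tabulated above rest on assumed values of g and E and are neither estimates nor limits.

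The consequence is limited to secondary IV volume and clearance outputs and to E_H and F_abs, which SAP 2.2 describes as additional parameters beyond the protocol's endpoint table. No primary endpoint is touched, and these results are summarised and listed without hypothesis tests. It should be corrected because a parameter reported for a secondary endpoint lacks a usable definition and clearance has an unreconciled dose.

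**What to change.** 1. In the V(c) row, name the volume intended and print the dimensionally correct formula that Phoenix implements, under the matching label. Alternatively, delete V(c) from Table 1, section 8.3.2, Tables 2.7 and 2.8 and Listing 34, and report V(dss).
2. In the CL(iv) row, replace the syringe-weight definition with the single radiometric Dose(IV) already specified for V and F, so that E_H follows on the same basis. Use one label for it throughout.
3. In the notes under Table 1, state that the radiometric dose is entered in Phoenix, or that CL and V from Phoenix are rescaled to it.

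The core cost is an edit to two table rows and one note; dropping V(c) also means removing it from the reporting entries above. If rescaling is chosen, it takes one dose ratio per participant, applied to CL and V, for six participants. No new samples, assays or visits are needed.
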